##### 4.3.1.1. Inclusion criteria

- Subject undergoing a percutaneous coronary intervention
- Subject 18 years of age or older, or of legal age to give informed consent per state or national law

##### 4.3.1.2. Exclusion criteria

- Subject undergoing an emergency treatment
- Primary angioplasty for acute ST segment elevation myocardial infarction.
- Subject with contrast allergies
- Subject with severe kidney disease (e-GFR < 40 by Modification of Diet in Renal Disease (MDRD)/Cockcroft Gault clearance formula and/or upon decision by investigator)
- Subject participates in a potentially confounding drug or device trial during the course of the study.
- Prisoners, people who cannot legally give consent, pregnant women and breastfeeding women

#### 4.3.2. Duration

The total duration of the study is expected to take approximately 4 months.

#### 4.3.3. Enrollment

Subjects are considered to be enrolled in the study after they have signed the informed consent form. No study procedures will be performed before this moment.

Subjects are enrolled in the study for the duration of the interventional procedure. No follow-up is required per protocol. Patient will be followed according to regular clinical standard of care.

#### 4.3.4. Number of subjects

It is expected that 45 subjects (see section 5 Statistical considerations) are necessary to collect sufficient data for the evaluation of the objectives of this clinical study. The enrollment period is expected to last for 4

Philips IGT Systems  Status: Final	Post-Market Clinical Study Plan  Contrast volume reduction during PCI with the use of Dynamic Coronary Roadmap	XCY607-130198 2017 Aug 15 Revision: 1.0 Page 10 of 16
---	---	--

months. There are no criteria for the amount of subjects treated with Dynamic Coronary Roadmap R1.1 versus R2.0, since a differentiating effect on this study's endpoints is not expected.

#### 4.3.5. Procedure for the replacement of subjects

Subjects in the study will not be replaced.

The data of these subjects will be analyzed (per intention to treat analysis, see section "statistical considerations").

#### 4.3.6. Subject withdrawal or discontinuation

Subjects can withdraw informed consent/data protection at any time during the study. There are no specific criteria for subject withdrawal or discontinuation

### 4.4. Procedures

Patients will receive standard medical treatment for their cardiac condition. During routine procedures, the physician may take angiograms for diagnosis which also serve as reference for device navigation. These angiograms will be automatically processed in the Dynamic Coronary Roadmap software and displayed as an overlay on the fluoroscopy for navigation support. In case a balloon catheter is used, the physician may take cine images when deflating the balloon as part of the standard care. These images can automatically be enhanced with the software and displayed. There is no follow up required after the procedure.

Phase 1: This is the phase where the physicians and study personnel can get used to the device and its capabilities. This phase serves to gain experience with the device and define workflow changes for the second phase. The use of Dynamic Coronary Roadmap makes these workflow changes possible and necessary in order to reduce the amount of contrast volume. It is estimated that 20 patients are necessary to gain enough experience and assess the workflow improvements.

Phase 2: This phase will focus on the contrast volume reduction. The defined workflow changes from phase 1 will be implemented in order to reduce the use of contrast volume. The minimal amount of contrast and timing of dosing will be defined. All other doses need to be avoided, as long as clinically acceptable. It is estimated that 25 patients are necessary to gain enough data to support the primary endpoint. This dataset will be compared with retrospective data from 25 patients that were treated without Dynamic Coronary Roadmap, preferably in the same timeframe.

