## 1. DEVICE DESCRIPTION

### 1.1. Summary description of the study device

The Dynamic Coronary Roadmap is developed by Philips Medical Systems Nederland B.V., a Philips Healthcare company. The proposed Dynamic Coronary Roadmap is a new software package that assists the imaging of the coronaries during coronary interventions.

Dynamic Coronary Roadmap Release 1.1 is a released software package (K170130) that can be used to support the navigation of interventional devices in the coronary arteries. Dynamic Coronary Roadmap allows the users to see a roadmap of the coronary anatomy displayed on live fluoroscopy. Dynamic Coronary Roadmap uses image registration techniques to provide an overlay of the coronary arteries (automatically derived from the coronary angiogram) on top of the live fluoroscopy (see Figure 1). It is intended to provide a Dynamic Coronary Roadmap for guidance and navigation of devices, providing additional confidence in the procedure, and possibly reducing the need for additional contrast puffs.

Dynamic Coronary Roadmap Release 2.0 introduces the FFR / iFR Roadmap feature. FFR/iFR Roadmap visualizes the position of the pressure wire and the coronary artery on an X-ray image at the moment that an intravascular blood pressure measurement was performed as well as the intravascular blood pressure measurement values themselves. Dynamic Coronary Roadmap Release 2.0 does not have 510(k) clearance yet.

Philips IGT Systems  Status: Final	Post-Market Clinical Study Plan  Contrast volume reduction during PCI with the use of Dynamic Coronary Roadmap	XCY607-130198 2017 Aug 15 Revision: 1.0 Page 6 of 16
---	---	---

Figure 1: On the left a standard fluoroscopy image and on the right a Dynamic Coronary Roadmap image with a coronary roadmap superimposed on a fluoroscopy image.

The study device includes the "Coronary tools" Dynamic Coronary Roadmap R1.1 and StentBoost Live R1.1 to permit full identification. Dynamic Coronary Roadmap R1.1 will be upgraded to R2.0 after FDA clearance of the FFR/iFR Roadmap feature.

[1] Note: StentBoost Live 1.1 is not used in the context of this post market study. Therefore it is not mentioned further in this post market study plan

The manufacturer of the study device is:

Philips Medical Systems Nederland B.V., a Philips Healthcare company  
[name]  
[name]  
The Netherlands

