### 1.2.1. Product Description Dynamic Coronary Roadmap [1]

Dynamic Coronary Roadmap is a software medical device intended to provide a real-time and dynamic angiographic roadmap of coronary arteries.

The angiographic roadmap is automatically generated from previously acquired diagnostic coronary angiograms during the same procedure.

Dynamic Coronary Roadmap overlays the angiographic roadmap on live 2D fluoroscopic images, thereby assisting the physician in navigating devices, e.g. (guide) wires, catheters, through the coronary arteries.

*Dynamic Coronary Roadmap is to be used in combination with a Philips interventional X-ray system.*

*When also used in conjunction with a compatible intravascular blood pressure measurement system, Dynamic Coronary Roadmap offers an FFR/iFR Roadmap feature which combines the information of the blood pressure within a coronary artery with an X-ray image of the pressure wire within that coronary artery, acquired when the pressure measurement was performed.*

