#### 1.2.5. General safety and effectiveness

To facilitate safe and effective operation of the system by a trained healthcare professional, instructions for use are provided as part of the device labeling.

Dynamic Coronary Roadmap is a software medical device and does not come in contact with a human subject.

The study device manual contains safety precautions and handling of the study device.

Note: the FFR / iFR Roadmap feature is disabled by means of a license in Dynamic Coronary Roadmap R1.1. The FFR / iFR Roadmap feature is enabled after upgrade to Dynamic Coronary Roadmap R2.0.

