### 1.3. Necessary training and experience needed to use the research device

Dynamic Coronary Roadmap is intended to be used and operated by adequately trained, qualified, and authorized healthcare professionals who have understanding of the safety information and emergency procedures as defined by local laws and regulations for radiation workers and staff. Training on the study device is needed and will be provided by Philips upon delivery of the device. This training will be documented and filed in the Investigator Site File.

Note: as ON/ OFF of the study device is not automatically coupled to the ON/OFF of the Allura system, the user will be trained and will get a dedicated version of the IFU. There are no other differences between the study device and the "regular Coronary Tools".

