### 4.5. Monitoring Plan

Monitoring will be performed by a trained person appointed by Philips to ensure compliance with the clinical study plan, applicable national regulations and international standards, patient safety and data validity. The Sponsor may designate one or more individuals to monitor the progress of a clinical study. The Sponsor may also delegate the monitoring responsibilities to a third party. However, the Sponsor remains ultimately responsible for the conduct of the study. The Institution is responsible for the appropriate de-identification of subject data. The investigational site should provide access to the source data of the subjects.

The first visit will occur as soon as possible after the first subject is enrolled at each study site. The monitoring schedule is based on the following considerations: enrollment rate, study compliance at the center, magnitude of data corrections required, study stage (e.g. start-up or follow-up), complexity of the study, IRB/MEC request, audit/inspection.

The monitor activities include:

- Check that the study is conducted, recorded and reported in compliance with this clinical study plan, and applicable regulations. Acts to oversee the progress of the study.
- Check signed and dated informed consent of the subjects and check that this is signed before any study-related procedures are undertaken.

Philips IGT Systems Status: Final	Post-Market Clinical Study Plan Contrast volume reduction during PCI with the use of Dynamic Coronary Roadmap	XY607-130198 2017 Aug 15 Revision: 1.0 Page 11 of 16
---	---	---

- Ensure that essential documents (e.g.contract, MEC approval) are maintained in the Investigator Site File.
- Ensure recording of deviations from protocol and store in Investigator Site File or CRF.
- Ensure that the principal investigator is informed and knowledgeable of all relevant document updates concerning the clinical study (e.g Clinical study plan). Ensure that amendments to the protocol are provided to the MEC/IRB by the principal investigator.
- Ensure device accountability and check unapproved use outside the study.
- No structural source data verification is anticipated.

Names of the monitor(s) can be found in *Appendix 10: List of monitor(s)/Clinical Scientist(s)* of this protocol. An update of this list can be provided to the site under separate cover.

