## 6. DATA MANAGEMENT

Electronic Case Report Form (e-CRF) will be used to collect medical history, subjects demographics, procedure related information, protocol deviations, adverse events and device deficiencies. The e-CRF will be used for data review, data cleaning and issuing and resolving queries. This e-CRF is a web-based e-CRF which is password protected and is 21 CFR part 11 compliant. At the end of the study the data will be stored as a frozen dataset and will be retained.

Raw image data is collected directly from the detector, and therefore is free from any subject information. All other exported data will be de-identified. This data will be collected and stored in a secure location.

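### Does the unnamed software that enhances balloon-deflation images in section 4.4 contradict the device description in section 1?

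*Protocol*

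**What the plan says.** Section 4.4 of the protocol, repeated in the Summary, describes two uses of images during the procedure. Diagnostic angiograms come first: "These angiograms will be automatically processed in the Dynamic Coronary Roadmap software and displayed as an overlay on the fluoroscopy for navigation support". The text then turns to balloon catheters. The physician may take cine images at deflation as routine care, and "These images can automatically be enhanced with the software and displayed".

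Section 1.2.1 gives the function of the device: "Dynamic Coronary Roadmap overlays the angiographic roadmap on live 2D fluoroscopic images, thereby assisting the physician in navigating devices". Release 2.0 adds the FFR/iFR Roadmap, and section 1.2 says this is the only difference in intended use between the releases. Sections 1.1 and 1.5 list StentBoost Live R1.1 as part of the study device, but the note in section 1.1 reads: "Note: StentBoost Live 1.1 is not used in the context of this post market study".

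Two further statements bear on what is switched on. Section 1.2.5 says that "the FFR / iFR Roadmap feature is disabled by means of a license in Dynamic Coronary Roadmap R1.1". Section 1.3, after describing how the device is powered on and off, says: "There are no other differences between the study device and the" regular product.

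**The concern.** The procedure text appears to allow something that the device description either omits or rules out. If the software meant is Dynamic Coronary Roadmap, section 4.4 relies on a function that section 1 never describes. If it is StentBoost Live, section 4.4 permits what the note in section 1.1 says is not done. Nothing states that StentBoost Live is disabled, whereas a licence lock is stated for the FFR/iFR feature in R1.1.

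What would be at stake is how such use is recorded. Section 8 forbids deviations and requires each one to be documented. Section 9 limits device use to what the plan provides. The monitor's first task in section 4.5 is: "Check that the study is conducted, recorded and reported in compliance with this clinical study plan". If one act is a permitted step in one section and excluded in another, site and monitor could classify it differently. One might also worry that a second imaging tool in Phase 2 would blur what a difference in contrast volume from the retrospective group is due to.

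**Working it through.** The plan gives no figure on this point, so there is nothing to reproduce. The check sets the passages side by side and then asks whether anything in the analysis depends on the answer.

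**Step 1: which software could be meant?**

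| Reading | Support in the protocol | What is then out of line |
|---|---|---|
| Dynamic Coronary Roadmap | The only software named in the same paragraph of 4.4, two sentences earlier | Sections 1.1 to 1.2.2 mention the overlay and, in R2.0, the FFR/iFR Roadmap, but no enhancement |
| StentBoost Live | The only other named component (1.1, 1.5) | The note in 1.1 says it is not used |
| The X-ray system itself | Named in 1.2.1 and 1.2.4 as the system the software works with | Nothing, but no passage gives it this function |

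PCI Express, in section 2.1, is only a name for the first two combined, so it adds no further candidate.

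The first reading is the natural one grammatically. It leaves a function out of the device description, but section 1.1 is headed as a summary and does not claim to list every function. Section 1.2.5 refers operation to the instructions for use and the device manual. The second reading needs an inference, because the protocol never says what StentBoost Live does.

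**Step 2: is there a firm contradiction?** Only on the second reading. Even there, the note sits with the identification of the device and explains why a listed component drops out of the plan. It can be read as setting the scope of the document rather than as a rule of conduct. It was not carried through consistently, since sections 1.5 and 2.1 name StentBoost Live again after the note says it will not recur. That points to loose editing.

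**Step 3: how many procedures?** Section 4.4 plans 20 patients in Phase 1 and 25 in Phase 2.

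- All procedures with the device: 20 + 25 = 45, so the number affected lies between 0 and 45.
- Phase 2 only, which is what section 5 analyses: between 0 and 25.

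The protocol does not say how often a deflation cine is taken or enhanced. Both ranges run from none to all and cannot be narrowed.

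**Step 4: does any analysis use it?**

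| Section | Endpoint | Refers to image enhancement? |
|---|---|---|
| 5.1 | Contrast volume in ml | No |
| 5.2.1 | Dose-area product (fluoroscopy, exposure, total) and total air kerma | No |
| 5.2.2 | Medical status and history, age, BMI, gender | No |
| 5.2.3 | Procedure time, time to first stent | No |
| 5.2.4 | Vessels, lesions, stents, access site, complexity, use of IVUS, OCT and FFR | No |

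The analysis set is every Phase 2 subject throughout, whatever display options were used. No subject enters or leaves an analysis because of the sentence in 4.4.

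**Step 5: does it affect the contrast comparison?** No passage says that enhancing a deflation cine saves or costs contrast. The cine is described as routine care, so the plan does not add an acquisition for the sake of the enhancement. The Phase 2 comparison already combines the software with the workflow changes defined in Phase 1, so it was never a comparison of the software alone. Section 3.1 calls the objective descriptive, with no pass or fail criteria.

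**The case for a change.** The strongest case for acting is that the fault can be shown from the text alone and is cheap to remove. Under either of the two named components some passage needs attention. StentBoost Live is installed, section 2.1 reports that it works together with Dynamic Coronary Roadmap, and nothing says it is locked. Device description and procedure belong in a protocol, so the point cannot be left to a statistical analysis plan. That the text only permits the enhancement is no full answer, because what one section permits should not be excluded by another.

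Most of this stands as a description of the wording. The claim about recording is weaker. A physician who does what the procedures section says the software can do is following the plan, so section 8 is not clearly triggered. Section 9 adds little, because StentBoost Live is listed as part of the study device. The absence of a statement that it is switched off contradicts nothing. If a site did want to note such use, the e-CRF described in section 6 already covers "procedure related information, protocol deviations, adverse events and device deficiencies". A dedicated entry per subject would collect an item that no planned analysis reads.

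**Conclusion.** The inconsistency is real but clerical. The Summary and section 4.4 leave the software unnamed, section 1 describes no matching function for Dynamic Coronary Roadmap, and the note in section 1.1 sets StentBoost Live aside. Naming the software, or dropping a permissive sentence, would leave the endpoints, the 45 planned subjects, the 25 analysed in Phase 2 and every summary in section 5 as they are. The effect on the planned analyses is nil, and the possible count of 0 to 45 procedures carries no information about harm.

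This rests on two assumptions: that enhancing a deflation cine does not itself change how much contrast is given, and that the instructions for use, which are not at hand, tell operators which component does what. The protocol contains nothing against the first, and section 1.2.5 supports the second. When the document is next revised, the sponsor can make the three places agree as a matter of editing. No change to the plan is called for.

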## SUMMARY

Identification of study device
The Dynamic Coronary Roadmap is developed by Philips Medical Systems Nederland B.V., a Philips Healthcare company. The proposed Dynamic Coronary Roadmap is a new software package that assists the imaging of the coronaries during coronary interventions.
Study design
This is a prospective, non-randomized, unblinded, observational, single-center study.
A non-randomized study design has been chosen to get first insights in contrast reduction with the use of Dynamic Coronary Roadmap. This study will serve as a pilot study to power a pivotal study at a later stage.
The results of the study population will be compared with retrospective data generated before the Dynamic Coronary Roadmap was installed.
Objectives
Primary objective: To collect data on the amount of contrast used during PCI with the aid of Dynamic Coronary Roadmap to define a possible contrast reduction. The study will serve as a pilot for potential larger and/or multi-center follow-up studies to define a possible contrast reduction claim.
Secondary objective(s):

 
Assessing radiation usage during PCI with the aid of Dynamic Coronary Roadmap
 
Collecting patient demographics to further define the study population
 
Assessing procedure efficiency
 
Collecting procedural information to further define the study population
 

Primary and secondary endpoints
The primary endpoint in this study will be the amount of contrast volume used during the PCI procedure.
Secondary endpoints will be the radiation dosage, procedure efficiency, study population and procedural information. This information will help to define the study population and/or procedures better and will be used to design a pivotal trial at a later stage.
Main inclusion criteria

 
Subject undergoing a percutaneous coronary intervention
 
Subject 18 years of age or older, or of legal age to give informed consent per state or national law
 
•
 

Main exclusion criteria

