Phase 2: This phase will focus on the contrast volume reduction. The defined workflow changes from phase 1 will be implemented in order to reduce the use of contrast volume. The minimal amount of contrast and timing of dosing will be defined. All other doses need to be avoided, as long as clinically acceptable. It is estimated that 25 patients are necessary to gain enough data to support the primary endpoint. This dataset will be compared with retrospective data from 25 patients that were treated without Dynamic Coronary Roadmap, preferably in the same timeframe.

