### 4.3. Subjects

#### 4.3.1. In- and exclusion criteria

Subjects participating in the study will be carefully selected based on the next inclusion and exclusion criteria.

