#### Sample size

To gain short term and long term user feedback on the usability and for the evaluation of the primary and secondary objectives of this clinical study, it is expected that approximately 45 patients will need to undergo a procedure with the study device.

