## 8. DEVIATIONS FROM THE CLINICAL STUDY PLAN

The Investigator is not allowed to deviate from the Clinical Study Plan or to enroll subjects that do not comply with all inclusion and exclusion criteria. Under emergency circumstances, deviations from the Clinical Study Plan to protect the rights, safety and well-being of human subjects may proceed without prior approval of the sponsor and the IRB. Such deviations shall be documented and reported to the sponsor and the IRB as soon as possible

All deviations from the Clinical Study Plan will be documented with date, subject, reason, actions taken and if the deviation affects subject's rights, safety and wellbeing or the scientific integrity of the clinical research. The deviation shall be notified to the Sponsor via the e-CRF as soon as possible. Deviations will be reviewed by the sponsor. In case of serious or repetitive deviations, a corrective action plan may be necessary. In some cases suspension of enrollment at the site or disqualification of the site is necessary.

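### The period of the 25 retrospective controls is worded inconsistently, and no eligibility or selection rule is stated for them

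*Protocol*

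**What the plan says.** **Control period.** The Summary, under study design, states: "The results of the study population will be compared with retrospective data generated before the Dynamic Coronary Roadmap was installed". Section 4.1 repeats this sentence. Section 4.4, on Phase 2, states: "This dataset will be compared with retrospective data from 25 patients that were treated without Dynamic Coronary Roadmap, preferably in the same timeframe". The Phase 2 paragraph of the Summary has the same text.

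**Who the criteria cover.** Section 4.3.1 opens: "Subjects participating in the study will be carefully selected based on the next inclusion and exclusion criteria". Section 4.3.3 adds: "Subjects are considered to be enrolled in the study after they have signed the informed consent form". Section 8 forbids the investigator to "enroll subjects that do not comply with all inclusion and exclusion criteria". The exclusions in 4.3.1.2 include "Subject undergoing an emergency treatment", primary angioplasty for ST-elevation infarction, and severe kidney disease (eGFR below 40). The kidney criterion also has a part left to the investigator's decision.

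**Numbers and purpose.** The sample size paragraph in 5.1 says "it is expected that approximately 45 patients will need to undergo a procedure with the study device". Section 4.4 splits these into about 20 in Phase 1 and 25 in Phase 2. Section 4.1 says the pilot is to power a later pivotal study. Sections 3.1 and 5.1 call the objective descriptive, with no pass or fail criteria.

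**The concern.** Any contrast reduction that this study reports will be the difference between the Phase 2 patients and the 25 controls. Which patients those controls are therefore matters as much as what is measured in Phase 2. The Protocol describes the control period in four places, and the two descriptions pull apart. It also gives no rule for choosing the individuals.

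Two things are at stake. The control group could have a different case mix from Phase 2, for instance by including urgent cases or patients with poor renal function that Phase 2 excludes. And the period or the individuals could be settled after contrast volumes are known. Either could distort the difference that is carried into the planning of the pivotal study.

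The source and eligibility of an external control group are design matters. The inconsistency lies within the Protocol itself, so a statistical analysis plan that is not at hand does not remove it.

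**Working it through.** **1. The Protocol's own total.** 20 (Phase 1) + 25 (Phase 2) = 45, as stated. All 45 are patients treated with the device. The 25 retrospective patients come on top of this number.

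**2. Can one control satisfy both period statements?**
- Statement A (Summary design paragraph, 4.1): the data arise before installation.
- Statement B (Summary Phase 2 paragraph, 4.4): treated without the device, preferably in the same timeframe. The sentence concerns the Phase 2 dataset.
- Phase 2 follows Phase 1, in which the device is already in use. If the timeframe means that of Phase 2, it falls wholly after installation and no patient meets both A and B.
- If it means a window close to the study but before installation, A and B agree. The text does not say this.

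**3. How far apart are the two readings?** Inputs: 45 subjects and a 4-month enrolment period (4.3.4). Even accrual is an assumption.
- Rate: 45 / 4 = 11.25 per month.
- Phase 1: 20 / 11.25 = 1.78 months. Phase 2: 25 / 11.25 = 2.22 months.
- The last pre-installation control precedes the first Phase 2 patient by at least 1.78 months.
- Distance between group midpoints = 1.78 + 2.22/2 + half the control window. This is 2.89 months for a window near zero, and 4.00 months if controls accrue at the study's rate (2.22/2 = 1.11 more).
- Controls treated during Phase 2 have no such gap, so the two readings select different patients. Nothing in the Protocol shows whether a gap of this length changes contrast use.

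**4. Do the eligibility rules reach the controls?** The criteria are addressed to participating subjects, enrolment is defined by signed consent, and section 8 restricts enrolment. The planned 45 are all device patients. A retrospective patient treated without the device is not enrolled in this sense. No sentence extends the criteria to such patients, and none mentions consecutive, random or matched selection or a calendar window.

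**5. Illustration of scale.** The Protocol gives no standard deviation (SD) for contrast volume, so this is in SD units with assumed inputs, not an estimate for this study.
- If k of 25 controls are of a kind excluded from Phase 2 and their mean differs by d SD from that of the other controls, the control mean shifts by (k/25) × d.
- With k = 5: d = 0.5 gives 0.10 SD, and d = 1.0 gives 0.20 SD.
- 95% confidence half-width for the difference, 25 against 25, common SD: t(48; 0.975) × √(2/25) = 2.011 × 0.2828 = 0.569 SD.
- Ratio of shift to half-width: 0.10/0.569 = 0.18 and 0.20/0.569 = 0.35.

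If the raw pilot difference were used to size the pivotal study (assumed: two-sample t-test, two-sided 5%, 80% power, true effect 0.50 SD), the planned sizes would be:

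| Shift | Effect seen | Planned n per arm |
|---|---|---|
| None | 0.50 SD | 64 |
| 0.10 SD | 0.60 or 0.40 SD | 45 or 100 |
| 0.20 SD | 0.70 or 0.30 SD | 34 or 176 |

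**The case against.** **The same-timeframe wording is only a preference.** One period is stated outright, and the other phrase is qualified and undefined. Read together, they can mean controls from before installation, as close in time as practicable. This stands. A reader might infer that the Protocol fixes two incompatible periods, but it does not go that far. What remains is that the window is never stated and the natural reading of the preference conflicts with the design statement.

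**The eligibility gap rests on silence.** No sentence admits emergency, infarction or low-eGFR patients as controls. This also stands. A reader might infer that the plan intends such controls or that the comparison is already biased, and the text supports neither. It only fails to rule them out.

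**The study is a descriptive pilot.** With no pass or fail criteria and an optional t-test, no formal error rate is at stake. Phase 2 also includes deliberate workflow changes to save contrast, so the comparison mixes device and workflow whichever controls are used. Both remarks lower the stakes. They do not remove them, because the stated use of the result is to power a pivotal study.

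**The illustration uses assumed inputs.** This is correct. Even its larger shift is about a third of the confidence half-width, so sampling error at 25 against 25 would be the larger source of uncertainty. Unlike sampling error, however, the confidence interval does not reflect a selection shift.

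**Procedural variables can be examined.** Section 5.2.4 notes that these are usually recorded for non-study patients too, so imbalance could be looked at. That helps interpretation but does not settle who the controls are. Tabulating them for both groups is reporting detail and no part of this point.

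**Conclusion.** The point holds as an inconsistency and an omission in the design text, and should be fixed. The Summary and 4.1 place the comparator before installation, while the Phase 2 text prefers a timeframe that most naturally falls after it. The 4.3.1 criteria are not applied to the 25 controls, and no selection rule is given. Controls with a different case mix, or chosen with contrast volumes in view, are therefore not ruled out.

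The direction and size of any resulting bias cannot be derived from the Protocol. The calendar figures (at least 1.8 months between the last pre-installation control and the first Phase 2 patient, and 2.9 to 4.0 months between midpoints) rest on even accrual. The shifts of 0.10 to 0.20 SD and the range of 34 to 176 per arm rest on assumed inputs and show only that the matter can be material for pivotal planning.

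**What to change.** - Reconcile the Summary (design and Phase 2 paragraphs), 4.1 and 4.4 to one control period. The window immediately before installation is one choice, and it fits the unqualified design statement. If the sponsor prefers controls from the Phase 2 period, the Summary design paragraph and 4.1 must change instead.
- State that the 25 controls are consecutive PCI patients in that window who meet the objective clinical criteria of 4.3.1. The part of the renal criterion left to the investigator's decision should not be used to select controls, since applied in retrospect it would reopen discretion over individual patients.
- State that controls are identified by procedure date before their contrast volumes are extracted.

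**Cost.** No additional patients are needed. The site must list PCI cases by date and check records for eligibility data such as eGFR. The change bears on the primary objective, so it does not fit section 7's category of non-significant changes and needs an amendment. If pre-installation controls are kept, a calendar gap of at least the length of Phase 1 remains, and differences over time are not removed.
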